3.6 Accompanying treatment

Allowing accompanying treatment

Medications that have been determined by the researchers to comply with the protocol (such as those used to treat disease-related symptoms and accompanying treatments for various AEs).

Subjects who need long-term medication due to basic diseases such as hypertension and diabetes can continue to use medication.

Allow local corticosteroid medication, such as topical use, eye drops, nasal spray, inhalation, etc.

Prohibited concomitant therapy

During the treatment period of this study, participants were prohibited from receiving the following treatments:

Biotherapy with anti-tumor effect (excluding cytokine drugs used to treat adverse events caused by chemotherapy drugs), and traditional Chinese patent medicines and simple preparations with anti-tumor effect

Drugs with immunomodulatory effects, including but not limited to non-specific immunomodulators (such as thymosin, interferon, interleukin, immunoglobulin, gamma globulin) and traditional Chinese patent medicines and simple preparations with immunomodulatory effects

Chemotherapy not specified in this plan

Live vaccine administration within 30 days prior to the first administration of Sintilimab and during the study process. Live vaccines include, but are not limited to, the following: measles, mumps, rubella, chickenpox, yellow fever, rabies, BCG vaccine, typhoid fever (oral) vaccine. Allow receiving inactivated virus vaccines for seasonal influenza; However, it is not allowed to receive attenuated live influenza vaccines administered intranasally.

Corticosteroids. Allow the use of inhaled steroids as part of fixed treatment for asthma or chronic obstructive pulmonary disease (COPD). Corticosteroids allowed for handling adverse events with potential immune causes. After consulting with the sponsor, the use of physiological doses of corticosteroids can be approved.

Note: The use of prophylactic corticosteroids is allowed to avoid allergic reactions (such as pre-treatment of intravenous contrast agents or chemotherapy drugs).

According to the evaluation of the researchers, subjects who need to use any of the above treatment methods for clinical treatment should be excluded from the trial. The subjects may accept other medication treatments deemed medically necessary by the researchers. It is important for researchers to review each medication (prescription and over-the-counter) received by participants before the start of the study and during each study visit.

During each visit, the subject must be asked about any new medications they have received.

To reduce the risk of adverse drug interactions, all measures must be taken to limit the number of concomitant medications that are truly necessary.

During administration, drugs with hepatotoxicity should be avoided (i.e. drugs with hepatotoxicity are warned in the product manual). Encourage researchers to review each potential hepatotoxic drug by searching the website www.livertox.nih.gov.

3.7 This study excluded the inclusion of vulnerable groups, such as individuals with mental illness, critically ill patients, pregnant women, illiterate individuals, minors, cognitive impairment individuals, students of PI or researchers, subordinates of PI or co researchers, employees of research institutions or sponsors.

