This study is a prospective single blind randomized controlled clinical trial of maintenance therapy with Xindilimab based on peripheral CD8TEX screening after standard radiotherapy and chemotherapy for locally advanced head and neck tumors. Synchronous radiotherapy and chemotherapy are routine standard treatments and do not require the use of immunotherapy drugs in this study. Blood samples were collected before and after radiotherapy, and participants were screened and evaluated according to the inclusion and exclusion criteria of the protocol within 28 days before randomization. Patients who

agree to participate in this study will sign an informed consent form (ICF) prior to the screening process. After completing all screening activities, eligible participants can start receiving study treatment. According to the estimated sample size, a total of 104 patients are planned to be enrolled and randomly assigned equally to the experimental group and control group. The treatment cycle for the study is 21 days. The experimental group starts treatment within one month after the end of radiotherapy and chemotherapy. On the first day of each cycle, intravenous treatment with Sintilimab is given, with a cycle of 21 days. It is expected to be administered for a total of 18 cycles, or until the disease progresses; The control group received placebo treatment. The experimental group underwent routine blood tests, liver and kidney function, myocardial enzyme spectrum, thyroid function, electrocardiogram every 2 cycles, and CT scans every 4 cycles to evaluate toxic side effects; The control group underwent the same frequency of follow-up and observation. The study started on January 1, 2024 and ended on January 1, 2027, to explore the efficacy of maintenance therapy with Xindilimab after radiotherapy and chemotherapy for locally advanced head and neck tumors.

Research plan:

Intravenous infusion of Sintilimab, D1, once every 3 weeks

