3.4.3 Efficacy evaluation

Inspection items	Inspection time and related instructions
Imaging examination	Complete baseline assessment within 1 month before treatment, and treat every 3 months Chest and abdominal CT examination evaluation

3.4.4 Testing items and time after discontinuation/withdrawal from the study (once every 9 weeks since the last medication use)

Inspection items	Inspection time and related instructions
Telephone follow-up	Telephone follow-up every two months

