c: For abnormal results in Level 4 laboratory tests, the decision to terminate medication should be based on accompanying clinical symptoms/signs and the researcher's clinical judgment.

The maximum interval allowed for drug suspension is 12 weeks. If the subject cannot recover to a state where they can reuse Sintilimab within 12 weeks, they will permanently discontinue Sintilimab and enter the follow-up phase. Excluding the following two situations:

1) Due to the use of glucocorticoids in the treatment of irAE, the process of reducing glucocorticoids resulted in the suspension of Sintilimab for more than 12 weeks. In this case, it is

necessary to discuss with the medical manager of the sponsor to decide whether to continue treatment with Sintilimab. The imaging examination for evaluating the therapeutic effect is carried out according to the plan and is not affected by the suspension of medication.

2) Due to the treatment of AE unrelated to Xindilimab, Xindilimab was temporarily suspended for more than 12 weeks. In this case, it is necessary to discuss with the sponsor to decide whether to continue treatment with Sintilimab. The imaging examination for evaluating the therapeutic effect is carried out according to the plan and is not affected by the suspension of medication.

The principle of restoring Sintilimab

When resuming the use of Sintilimab, relevant AEs need to be restored to level 0-1 or baseline, with an ECOG PS score of 0-1.

Management of infusion reactions related to Sintilimab

Xindilizumab may cause severe or life-threatening infusion reactions, including severe hypersensitivity or allergic reactions. Signs and symptoms usually appear during or shortly after drug infusion, and can usually be completely resolved within 24 hours of completion of infusion.

The management guidelines for infusion reactions associated with Sintilimab are shown in Table 2.

NCI CTCAE classification	Treatment	Perform pre-treatment medication during subsequent administration
Grade 1 Mild reactions; No need to interrupt infusion; No intervention required	According to the patient's medical indications, strengthen monitoring of their vital signs until the researchers believe that the subject's condition is stable.	None

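### Section 3.6 tells sites to exclude from the trial any patient who needs a prohibited treatment, which can end imaging before progression is documented and censor PFS informatively

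*Protocol*

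**What the plan says.** Section 3.6 opens its list of prohibited concomitant therapy with "During the treatment period of this study, participants were prohibited from receiving the following treatments". The list includes biotherapy with anti-tumour effect, "Chemotherapy not specified in this plan", and "Drugs with immunomodulatory effects, including but not limited to non-specific immunomodulators". Corticosteroids are also listed, with exceptions; one reads "Corticosteroids allowed for handling adverse events with potential immune causes". The section closes with the disposition: on the researchers' evaluation, "subjects who need to use any of the above treatment methods for clinical treatment should be excluded from the trial".

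Three other places bear on what happens to a patient who cannot continue:

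- Section 3.5.2, text after the table: patients who cannot restart within 12 weeks of a suspension: "they will permanently discontinue Sintilimab and enter the follow-up phase".
- Section 3.3, on treatment duration: "It is expected to be administered for a total of 18 cycles, or until the disease progresses".
- Section 3.4.4 is headed "Testing items and time after discontinuation/withdrawal from the study (once every 9 weeks since the last medication use"). Its only entry is a telephone call every two months.

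The primary endpoints in section 2.2 are PFS and 1-year PFS by RECIST 1.1.

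**The concern.** The prohibition runs through the treatment period, so the rule reaches randomised patients. A need for other anti-tumour therapy is seldom unrelated to prognosis: a patient may be deteriorating clinically between two scans that are about 12 weeks apart. If that patient is excluded from the trial and not merely taken off study drug, the study may never record the progression that was coming. PFS is then censored because an event was near, which is the situation in which the usual assumption of non-informative censoring fails.

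The decision rests on the researchers' evaluation, and the trial is described as single blind without saying who is blinded. If the person deciding knows the arm, exclusion could differ between arms for that reason too.

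This is a rule of conduct. An analysis plan can define analysis sets and censoring, but it cannot recover scans that were never taken.

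**Working it through.** **1. The passages side by side**

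| Situation | Stated disposition | Imaging afterwards |
|---|---|---|
| Suspension not resolved within 12 weeks (text after the 3.5.2 table) | Stop sintilimab, enter follow-up | Not stated for this group; planned imaging continues for the two excepted kinds of long suspension |
| Discontinuation or withdrawal (3.4.4) | Telephone follow-up | None listed |
| Need for a prohibited treatment (3.6) | Exclusion from the trial | None stated |

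Section 3.6 does not say whether its excluded patients enter the 3.4.4 schedule. Even if they do, that schedule holds only telephone contact, and RECIST 1.1 progression cannot be assessed by telephone.

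**2. How much of the endpoint window the rule covers**

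Eighteen cycles of 21 days (section 3.3) is 18 × 21 = 378 days. For a patient who stays on treatment, the prohibition is in force for the whole of the first year, the horizon of the 1-year PFS endpoint. Scans every 4 cycles are 4 × 21 = 84 days apart, in line with the 3 months given in section 3.4.3.

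**3. Illustration of the effect on the hazard ratio**

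Inputs from the protocol: 104 patients randomised equally, so 52 per arm (section 3.3); 3-year PFS of about 60% (section 1). The protocol gives no error rate, power or effect size from which 104 could be reproduced; the point does not depend on it.

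Assumptions: exponential PFS, 36 months of observation for everyone, control 3-year PFS of 60%, and a fraction f of would-be events in an arm removed and censored just before they are documented. The fractions are assumed; the protocol offers none.

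Observed HR (sintilimab versus placebo) = true HR × (1 − f_sintilimab) / (1 − f_placebo)

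| True HR | f placebo | f sintilimab | Observed HR |
|---|---|---|---|
| 1.0 | 10% | 10% | 1.0 |
| 1.0 | 20% | 10% | 0.90/0.80 = 1.125 |
| 1.0 | 10% | 20% | 0.80/0.90 = 0.889 |
| 0.6 | 20% | 10% | 0.6 × 1.125 = 0.675 |
| 0.6 | 10% | 20% | 0.6 × 0.889 = 0.533 |

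With equal loss and a true HR of 1.0, events over 36 months are 2 × 52 × 0.40 = 41.6 with no removal, 41.6 × 0.9 = 37.4 at f = 10%, and 41.6 × 0.8 = 33.3 at f = 20%.

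**4. Effect on 1-year PFS**

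Under the same model, true 1-year PFS in the control arm is 0.60^(1/3) = 84.3%. The observed value is 0.60^((1 − f)/3): 85.8% at f = 10% and 87.3% at f = 20%.

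Expected first-year events per arm are 52 × (1 − 0.843) = about 8. Losing one or two of them in an arm is about 12% to 25% of that arm's first-year events, so a handful of exclusions would be enough to reach the fractions assumed above.

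**The case against.** Much can be said for the protocol, and several stronger conclusions that a reader might draw do not follow.

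- **Overall survival.** A reader might infer that exclusion ends survival follow-up. Section 3.4.4 provides telephone contact after withdrawal from the study, and telephone contact can capture deaths. What stands is only that the protocol does not say whether excluded patients enter that schedule.
- **Serious toxicity.** A reader might infer that the patients with the worst immune toxicity vanish from the safety data. Corticosteroids for possible immune-related events are expressly allowed, and unresolved suspensions lead to follow-up. The remaining route is narrow: agents such as immunoglobulin, for which no adverse-event exception is stated. Even there the triggering event precedes the exclusion, and section 3.8 requires a completed case report form for every subject who consented and passed screening. At most, later events could be missed.
- **Progression.** Treatment runs until progression, so therapy given after documented progression normally falls outside the treatment period and after the PFS event. This objection stands, and it confines the point to therapy started before progression is documented.
- **Strength of the rule.** The text says should, not must, and leaves the judgement to the researchers. Leaving the trial is also not the same as removal from the analysis; analysis sets and censoring rules may be in the analysis plan, which is not shown.
- **Contradiction.** Sections 3.5.2 and 3.6 have different triggers, so they do not strictly contradict each other. They still give unlike dispositions to randomised patients who cannot continue.

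None of this answers the central gap: after exclusion, no study imaging is provided for.

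**Conclusion.** The point holds in a limited form. Section 3.6 runs together stopping study drug and leaving the trial. For patients who start other anti-tumour therapy before RECIST 1.1 progression is documented, this can censor the primary PFS endpoint informatively, because even the most favourable reading leads to a schedule without scans.

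It is a risk created by the wording, not a demonstrated bias. Its size and direction are unknown. The hazard ratios above rest wholly on assumed fractions, and the shift in the hazard ratio also needs those fractions to differ between arms. The documents do not support a claim that PFS, overall survival and safety are all biased. The wording should be corrected, since imaging not done cannot be recovered later.

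**What to change.** Reconcile section 3.6 with section 3.4.4 and with the text after the table in section 3.5.2. The closing rule of 3.6 could read:

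> Patients who need a prohibited treatment after randomisation remain in the trial in their randomised group. Scheduled tumour imaging continues until RECIST 1.1 progression, and safety and survival follow-up continue. The start date of any new anti-tumour therapy is recorded.

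Keep the word excluded for patients identified before randomisation. Add imaging to section 3.4.4 for patients without documented progression. What happens to study drug when a prohibited treatment is needed is for the sponsor to state; no rule is proposed here.

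The cost is a few sentences, a clear case report form field for the start date (concomitant medication is already asked about and recorded under sections 3.6 and 3.8), and continued scheduled scans for a few patients on other therapy. With the scans and the date in hand, the analysis can either count progression after new therapy or censor at its start.

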3.8 Data Management and Confidentiality

The data collected during the study period will be recorded in the subject's personal case report form. Each subject is assigned a unique subject number in the case report form for

identification. Any data modifications made by data entry personnel in the case report form system will be automatically recorded through the system's "audit trail" function.

The data entry personnel should fill out the case report form as soon as possible after follow-up, and any questions should be answered as soon as possible to maintain the latest data. The case report form should be completed, reviewed, and signed by the researcher as soon as possible after the last follow-up of the subjects. Each subject who has signed the ICF and passed all screening steps must have a completed case report form. If the subject did not receive treatment, the reason must be recorded in the case report form. All data outside of the case report form (laboratory tests, imaging examinations) will be integrated with the relevant data in the subject's case report form. The subject number and date of participation in the study should be recorded by the researcher in the subject's medical/research file along with the study code. Researchers should also record the following information in their medical/research records: written and oral confirmation of informed consent, clinical status of the subjects, dates of each study follow-up, dates of study drug administration, concomitant medications, copies of all relevant reports and laboratory test results, opinions on the results, and any AEs mentioned. The researcher completes electronic signatures through the system in the case report form, which indicate that the researcher has checked or reviewed the data, data questions, and research center notices on the case report form, and agrees to the relevant content. All information and other materials used by subjects and researchers must use clear and understandable vocabulary and language.

The medical records, imaging data, drug use registration form, subject code table, serious adverse event report form and other data of the subjects are kept confidential, and these materials are not disclosed to the public outside the scope permitted by relevant laws and/or regulations. The drug regulatory department, the sponsor, and their authorized supervisory personnel, as well as the ethics committee, have the right to access relevant trial data and original records with the consent of the main researchers involved in the trial.

4. Informed consent

Before participants participate in the study, the researcher is responsible for fully explaining the research purpose, methods, expected benefits, and potential hazards to the participants, in order to further obtain voluntary written consent from the participants or their guardians (if permitted by local regulations). The legal representative refers to an individual or institution who, in accordance with legal requirements and with the authorization of the subject or the law, can make consent on behalf of the subject to participate in clinical research. ICF should be written in the native language of the potential subject population.

Researchers should comply with relevant regulatory requirements, GCP, and ethical principles derived from the Helsinki Declaration to obtain written consent from participants. Before providing ICF and its revised versions to potential subjects, approval from IEC/IRB should be obtained. Researchers should ensure that each participant is informed that they can voluntarily terminate the study at any time, and that each participant has the opportunity to ask questions and have time to reflect on the information obtained.

The ICF should be obtained before the participants participate in the study and the consent form should be kept in the research center as a document. The ICF should be signed by the subject themselves or their legal representative (if permitted by local regulations), as well as the researcher's name and date. The original signed ICF should be kept at the research center and a copy of the signed consent form should be provided to the subject or their legal representative. The date of obtaining informed consent should be recorded in the medical records and original records.

If the subject or their legal representative (if permitted by local regulations) lacks reading ability, a fair witness should be present throughout the informed consent discussion process. Witnesses should sign the ICF after the subject or their legal representative agrees to participate in the study and signs the ICF (if possible). Signing the ICF indicates that the witness confirms that they have fully explained the information and any other written information in the ICF to the subject or their legal representative, that they have clearly understood the information, and that the subject or their legal representative agrees to sign the written ICF.

The following vulnerable groups with informed consent were excluded from this study, such as:

- (1) Patients, especially hospitalized and mentally ill patients with serious illnesses: those who have no capacity for behavior shall have their legal guardians sign.
- (2) Prisoners, pregnant women, intellectually disabled individuals, and other individuals who may be economically or educationally disadvantaged
- (3) Children: must obtain an informed consent form signed by their legal guardian; When children can actually make a decision to agree to participate in the study, they must obtain their consent
- (4) Students, staff members of this institution, etc.: Participating in research conducted by their management personnel shall not have any additional benefits, and shall not be forced to participate;
- (5) Notes on obtaining informed consent for patients with mental/cognitive impairments:

7. Reporting of Adverse Events

7.1 Definition of Adverse Events

Adverse Event (AE) is defined as any adverse medical event that occurs in a clinical study after a subject receives treatment with a certain drug, regardless of whether it is causally related to the investigational drug. AE includes but is not limited to the following situations:

- The worsening of the original medical condition/disease (including symptoms, signs, and laboratory test abnormalities) before entering clinical trials;
- Any newly occurring adverse medical conditions (including symptoms, signs, newly

diagnosed diseases);

- Abnormal laboratory test values or results with clinical significance.

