The primary safety analysis will be conducted based on subjects who experience toxicity (as defined by CTCAE standards). CTCAE version 5.0 will be used to evaluate safety through reported adverse events. The relationship between adverse events and drugs, onset time, duration of events, their resolution, and any concomitant medication will be recorded. Adverse events (AEs) will be analyzed, including but not limited to all AEs, SAEs, lethal AEs, and laboratory changes.

2.4 Exploratory study endpoint:

Explore biomarkers for predicting efficacy and adverse reactions, and obtain better guidance on the combination therapy and safety of immunotumor drugs. In order to identify novel biomarkers, we collected biological samples: 10-20ml of blood (before treatment and during efficacy evaluation) to support the analysis of cellular components (such as DNA, proteins, etc.), such as whole exome gene testing, TMB, PD-L1, MRD, etc.

3. Research design and methods:

3.1 Inclusion criteria:

- (1) Male or female, age ≥ 18 years old, ≤ 75 years old.
- (2) Localized advanced head and neck tumors with T3 or N+ or above that have been histologically confirmed as inoperable.
- (3) Patients undergoing synchronous radiotherapy and chemotherapy
- (4) ECOG physical fitness status ranges from 0 to 1 point.
- (5) The expected lifespan is at least 12 weeks.
- (6) At least one measurable lesion
- (7) Hematology examination absolute neutrophil count (ANC) $>1.5 \times 10^9/L$, hemoglobin $>8g/dL$ and platelets $>100 \times 10^9/L$ (based on the normal value of the clinical trial center).
- (8) Prothrombin time (PT) <1.5 times the upper limit of normal value and normal thromboplastin time (APTT) <1.5 times the upper limit of normal value.
- (9) Laboratory tests show that serum creatinine is less than or equal to 1.5 times the upper limit of the normal reference range (if serum creatinine increases, 24-hour urine must be collected, except for those with a 24-hour creatinine clearance rate $>50ml/min$).

- (10) When there is no liver metastasis, ALT or AST is less than or equal to 2.5 times the upper limit of the normal reference range, and serum total bilirubin is less than or equal to 1.5 times the upper limit of the normal reference range; For patients with liver metastasis, ALT or AST is less than or equal to 5 times the upper limit of the normal reference range, and serum total bilirubin is less than or equal to 3 times the upper limit of the normal reference range.

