7.2 Definition of serious adverse events

Serious Adverse Event (SAE) refers to an adverse event that meets at least one of the following criteria:

- Causing death, excluding deaths caused by disease progression based on research indications.
- Life threatening (defined as "life-threatening" refers to an AE where the subject is at risk of death when it occurs, but does not include an AE that could potentially cause death if the event worsens).
- Hospitalization treatment or extended hospital stay is required, excluding the following situations:
 - ✓ Rehabilitation institutions
 - ✓ Sanatorium
 - ✓ Routine emergency room admission
 - ✓ Same day surgery (such as outpatient/same day/non bed rest surgery)

Hospitalization treatment or prolonged hospital stay that is not related to the deterioration of AE itself is not an SAE. For example, if admitted due to an existing disease, there have been no new adverse events or worsening of the existing disease (such as in order to check for laboratory test abnormalities that have persisted since the trial); Hospitalization for management reasons (such as annual routine physical examinations); Hospitalization specified in the trial protocol during the clinical trial period (such as operating according to the requirements of the trial protocol); Selective hospitalization unrelated to the worsening of adverse events (such as elective surgery); The scheduled treatment or surgical procedure should be included in the entire trial protocol and/Or record in the baseline data of the individual subject; Admitted solely for the use of blood

products.

- Causing permanent or severe disability/loss of ability.
- Causing congenital abnormalities/birth defects.
- Other important medical events: defined as events that harm subjects or require medical intervention to prevent the occurrence of any of the above situations.

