7.3 Evaluation of Adverse Events

Researchers will evaluate all adverse events according to the NCI Common Terminology for Adverse Events (CTCAE) version 5.0. Any adverse events that change the CTCAE level will be recorded in the adverse event case report form/worksheet.

All adverse events, regardless of CTCAE level, must be evaluated for severity.

Various adverse events: Take timely measures to handle and record in the case report form.

Serious adverse events (SAE): Take timely measures to handle, record in the case report form, decide to stop or reduce medication by the researcher, immediately report to the ethics committee, drug clinical trial institution, and sponsor, and report to the national and provincial food and drug regulatory authorities within 24 hours. SAE must log in to the "Non Responsibility Reporting System for Adverse Events and Similar Errors within the Hospital" to report. Specific process: see the following figure

Serious adverse events occur (requiring hospitalization, prolonged hospitalization, disability, affecting work ability, endangering life or death, causing congenital malformations, etc.)

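### Progression of the study cancer is exempt only from the SAE death criterion, so it still counts as an AE, and as an SAE when it leads to admission, in the all-cause safety comparison

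*Protocol*

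**What the plan says.** - **Protocol 7.1.** An AE is any adverse medical event after treatment with a drug, "regardless of whether it is causally related to the investigational drug". The first listed example is "The worsening of the original medical condition/disease (including symptoms, signs, and laboratory test abnormalities) before entering clinical trials". No exception is made for the study cancer.
- **Protocol 7.2.** An SAE "refers to an adverse event that meets at least one of the following criteria". The death criterion reads "Causing death, excluding deaths caused by disease progression based on research indications". The next criteria carry no such exemption. Hospitalisation reads "Hospitalization treatment or extended hospital stay is required, excluding the following situations", and the situations then listed are rehabilitation institutions, sanatoria, routine emergency admission and same-day surgery. A further carve-out covers admission for a disease already present, but on the condition that "if admitted due to an existing disease, there have been no new adverse events or worsening of the existing disease".
- **Protocol 2.3.** Safety and tolerability are secondary endpoints: "Adverse events (AEs) will be analyzed, including but not limited to all AEs, SAEs, lethal AEs, and laboratory changes". The lethal category is not defined. The relationship of each event to drug is recorded.
- **Protocol 2.2.** The primary endpoint is PFS and 1-year PFS by RECIST 1.1.
- **Protocol 7.3.** Every SAE goes at once to the ethics committee, the trial institution and the sponsor, and to the authorities within 24 hours.

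**The concern.** For every participant the disease present before entry is the study cancer, so its worsening fits the first AE example in 7.1. The exemption in 7.2 shows that the authors did not want progression deaths counted as serious, but it stops at death. The less severe outcome of the same process, an admission, is then serious where the death is not.

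Two things are at stake. First, progression is the primary endpoint. If it also enters the all-cause AE and SAE counts, the safety comparison carries part of the efficacy result. Events common to both arms dilute a true excess on sintilimab. If sintilimab delays progression, placebo collects more of them and the excess shrinks further. Second, admissions for progression would enter the 24-hour reporting stream.

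**Working it through.** **Reading the rules together**

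1. *Progression with worse signs or symptoms.* It is a worsening of the pre-entry disease, cause is irrelevant, and 7.1 has no exemption. It is an AE.
2. *Admission for that progression.* One criterion is enough, admission is a criterion, and progression is not among its exclusions. The existing-disease carve-out does not help, because it requires that the disease has not worsened. It is an SAE.
3. *Progression that is life-threatening or disabling.* These criteria carry no progression exemption either. It is an SAE.
4. *Death from progression.* It is not serious under the death criterion. If an admission for the progression came first, step 2 still applies.
5. *Lethal AE under 2.3.* The term is undefined. 7.1 would let a fatal progression in; the only text on fatal progression, in 7.2, points the other way. This is open.

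**Size, as an illustration at 1 year**

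The protocol gives no SAE rates, so there is no plan figure to reproduce.

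Inputs:
- From the protocol introduction: 3-year PFS about 60%, read here as exponential and used for the control arm.
- Assumed: true SAE rates apart from progression of 20% on sintilimab and 12% on placebo (risk ratio 0.20/0.12 = 1.67, difference 8 points).
- Assumed: a share h of 30% to 70% of patients with a PFS event is admitted for it.
- Assumed: PFS hazard ratio (HR) of 1 (no efficacy) or 0.6.
- Assumed: PFS events are treated as progressions, and are independent of other SAEs.

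PFS events by 1 year:
- Control: 1 - 0.60^(1/3) = 15.7%
- Sintilimab at HR 0.6: 1 - (1 - 0.157)^0.6 = 9.7%

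Observed SAE rate = 1 - (1 - true rate) x (1 - PFS-event rate x h):

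| HR | h | Placebo | Sintilimab | Risk ratio | Difference (points) |
|---|---|---|---|---|---|
| none counted | - | 12.0% | 20.0% | 1.67 | 8.0 |
| 1 | 30% | 16.1% | 23.8% | 1.47 | 7.6 |
| 1 | 70% | 21.6% | 28.8% | 1.33 | 7.1 |
| 0.6 | 30% | 16.1% | 22.3% | 1.38 | 6.2 |
| 0.6 | 70% | 21.6% | 25.4% | 1.18 | 3.8 |

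Example, HR 0.6 and h = 70%: placebo 1 - 0.88 x (1 - 0.1566 x 0.7) = 0.216; sintilimab 1 - 0.80 x (1 - 0.0971 x 0.7) = 0.254; ratio 1.18.

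The horizon is kept at 1 year because planned treatment is 18 x 21 = 378 days or until progression, and the visible text gives no AE collection window.

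**The case against.** The strongest case against is that this is a narrow drafting gap.

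- *The relationship to drug is recorded, and 2.3 bases the primary safety analysis on toxicity.* This stands in part. Tables of drug-related events would largely separate progression from toxicity, so the distortion concerns all-cause totals. But 2.3 also calls for all AEs and SAEs.
- *The illustration rests on assumed rates.* This stands. It shows direction and plausible order, not an estimate for this trial. With no efficacy the risk difference barely moves (8.0 to 7.6-7.1 points).
- *A SAP could deal with it.* Only partly. A SAP can filter tables, but 7.1 and 7.2 decide what sites record and report within 24 hours.

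Three stronger readings are tempting, and the protocol does not support them:

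- A reader might infer that progression deaths are certainly lethal AEs and would make up most of that category. The term is undefined, and the death exemption in 7.2 tells against that reading.
- A reader might infer that 7.3 contradicts 7.2, because its process box, "Serious adverse events occur (requiring hospitalization, prolonged hospitalization, disability, affecting work ability, endangering life or death, causing congenital malformations, etc"), names death without the exemption. The box is a summary at the head of a flow chart. It starts from an SAE having occurred, and so presupposes the 7.2 definition.
- A reader might add the whole difference in progression to the AE risk difference, or carry the figures to years 2 and 3. The first ignores that many progressing patients will have another AE anyway. The second assumes AE capture well past the 378-day treatment period.

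**Conclusion.** The point holds as an inconsistency between 7.1, 7.2 and 2.3. On the wording, progression of the study cancer is an AE and an admission for it is an SAE, although death from it is exempt under the death criterion. Whether such deaths are lethal AEs is left open.

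The consequence is dilution of any sintilimab excess in the all-cause comparisons, and partial masking if sintilimab delays progression. On the stated assumptions a true SAE risk ratio of 1.67 would be seen at 1 year as about 1.47-1.33 with no efficacy and 1.38-1.18 at HR 0.6. The size depends on the admission share, the true SAE rates, the hazard ratio and the AE collection window. Masking is thus a possibility, not a demonstrated result.

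**What to change.** Reconcile the three sections in one amendment:

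1. In 7.1, state that progression of the study head and neck cancer, and signs or symptoms due to it alone, are efficacy outcomes and are not recorded as AEs.
2. In 7.2, move the progression exemption from the death criterion to the head of the list, so that it covers every criterion.
3. In 2.3, state that lethal AEs follow the same rule.
4. Tabulate all deaths by arm and cause, whatever their AE status.

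The cost is a few sentences and one table. The downside is that attribution to progression rests on the investigator, so a toxic death could be put down to the cancer. The deaths table keeps such a case visible.
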